## **Contraception guidance for male participants with partner(s) of childbearing potential**

Male subjects with female partners of childbearing potential are eligible if they agree to the following during the treatment and until the end of relevant systemic exposure, defined as 4 months after the last dose of study treatment.

- Inform any and all partner(s) of their participation in a clinical drug study and the need to comply with contraception instructions as directed by the investigator.
- Male subjects are required to use a condom during study duration and until end of relevant systemic exposure, defined as 4 months after the last dose of study treatment.
- Female partners of males subjects in the study to consider use of effective methods of contraception until the end of relevant systemic exposure, defined as 4 months after the last dose of treatment in the male participant.

Male subjects with a pregnant or breastfeeding partner must agree to remain abstinent from penile-vaginal intercourse or use a male condom during each episode of penile penetration during the treatment and until 4 months after the last dose of study treatment. Refrain from donating sperm for the duration of the study treatment and until 4 months after the last dose of study treatment.

## Appendix E: Potential Drug Interactions with Cabozantinib

| Strong Inhibitors of CYP3A4  | Strong Inducers of CYP3A4  |
|--|--|
| 
Antivirals
 
 
Boceprevir
 
Cobicistat
 
Conivaptan
 
Danoprevir
 
Dasabuvir
 
Elvitegravir
 
Indinavir
 
Lopinavir
 
Nelfinavir
 
Ombitasvir
 
Paritaprevir
 
Ritonavir
 
Saquinavir
 
Telaprevir
 
Tipranavir
 
 
Anti-Fungals
 
 
Itraconazole
 
Ketoconazole
 
Posaconazole
 
Voriconazole
 
 
Antibiotics
 
 
Clarithromycin
 
Telithromycin
 
Troleandomycin
 
 
Conivaptan
Diltiazem
Grapefruit Juice
Idelalisib
Nefazodone
 | 
 
Carbamazepine
 
Efavirenz
 
Enzalutamide
 
Erythromycin
 
Mitotane
 
Modafinil
 
Nevirapine
 
Oxcarbazepine
 
Phenytoin
 
Rifampin
 
St. John's wort
 
 |

This table is not all-inclusive. Please refer to the Flockhart drug interaction tables and FDA websites for the most updated lists of substrates, inducers, and inhibitors of selected CYP450 isozyme pathways:

<http://medicine.iupui.edu/clinpharm/ddis/table.aspx>

<http://www.fda.gov/Drugs/DevelopmentApprovalProcess/DevelopmentResources/DrugInteractionsLabeling/ucm080499.htm>.

## Appendix F: ECOG Performance Scale

| Score | Description   |
|-------|---|
| 0     | Normal activity. Fully active, able to carry on all predisease performance without restriction.   |
| 1     | Symptoms, but ambulatory. Restricted in physically strenuous activity, but ambulatory and able to carry out work of a light or sedentary nature (eg, light housework, office work). |
| 2     | In bed < 50% of the time. Ambulatory and capable of all self-care, but unable to carry out any work activities. Up and about more than 50% of waking hours.                         |
| 3     | In bed > 50% of the time. Capable of only limited self-care, confined to bed or chair more than 50% of waking hours.  |
| 4     | 100% bedridden. Completely disabled. Cannot carry on any self-care. Totally confined to bed or chair.   |
| 5     | Dead  |

## **Appendix G: Guidelines for Best Supportive Care**

The following general guidelines should be utilized to provide subjects with BSC:

### ***Analgesia***

- Pain assessment with prescriptions for nonnarcotic or narcotic analgesics, as required, except that nonsteroidal anti-inflammatory agents should not be used in treatment of pain, because they are known to induce renal failure in patients with decompensated liver disease
- Management of toxicities from analgesic medication including constipation, nausea or gastritis

### ***Treatment of infections***

- Antibiotics for peritonitis, pneumonia and other infections, as required

### ***Nutritional support***

### ***Psychological support***

- Management of depression and anxiety by medication and/or counseling as clinically appropriate

### ***Anemia***

- Transfusions may be given to maintain hemoglobin as clinically indicated, but erythroid growth factors should not be used

## Appendix H: Response Evaluation Criteria in Solid Tumors Version 1.1

Adapted from Eisenhauer 2009

### Definitions

Baseline: Baseline is defined as the most recent assessment performed prior to randomization. Baseline assessments must be performed within the period defined in the protocol eligibility criteria.

Measurable lesions: Except for lymph nodes as described below, measurable lesions are defined as those that can be accurately measured in at least 1 dimension (longest diameter to be recorded) as  $\geq 10$  mm with CT scan (if CT scans have slice thickness greater than 5 mm the minimum size for a measurable lesion is twice the slice thickness).

- To be considered pathologically enlarged and measurable, a lymph node must be  $\geq 15$  mm in short axis when assessed by CT scan (CT scan slice thickness recommended to be no greater than 5 mm). At baseline and in follow-up, only the short axis will be measured and recorded.
- MRI may be substituted for contrast-enhanced CT for lesions at some anatomical sites, but not for lesions in the lungs. The minimum size for measurability is the same as for CT (10 mm) as long as the scans are performed with slice thickness of 5 mm and no gap. If MRI is performed with thicker slices, the size of a measurable lesion at baseline should be twice the slice thickness. In the event there are interslice gaps, this also needs to be considered in determining the size of measurable lesions at baseline.

Nonmeasurable lesions: All other lesions (or sites of disease), including small lesions (longest diameter  $< 10$  mm or pathological lymph nodes with  $\geq 10$  to  $< 15$  mm short axis), are considered nonmeasurable. Lymph nodes that have a short axis  $< 10$  mm are considered nonpathological and are not be recorded or followed. Bone lesions, leptomeningeal disease, ascites, pleural/pericardial effusions, lymphangitis cutis/ pulmonitis, inflammatory breast disease, and abdominal masses (not followed by CT or MRI), are considered as nonmeasurable.

Target lesions: All measurable lesions up to a maximum of 2 lesions per organ and 5 lesions in total, representative of all involved organs, are to be identified as **target lesions** and measured and recorded at baseline. Target lesions are to be selected on the basis of their size (lesions with the longest diameter), be representative of all involved organs, and be those that lend themselves to reproducible repeated measurements. It may be the case that, on occasion, the largest lesion does not lend itself to reproducible measurement in which circumstance the next largest lesion which can be measured reproducibly should be selected. Target lesions will be measured at each assessment (longest axis for nonnodal lesions, shortest axis for measurable malignant nodal lesions).

Nontarget lesions: All other lesions (or sites of disease) including all non-measurable lesions (including pathological lymph nodes with  $\geq 10$  to  $< 15$  mm short axis) and all measurable lesions over and above the 5 target lesions are to be identified as **non-target lesions** and recorded at baseline. Measurements of these lesions are not required, but the presence, absence, or in rare cases unequivocal progression of each is to be recorded throughout follow-up. Lymph nodes that have a short axis  $< 10$  mm are considered non-pathological and are not to be recorded or followed.

To be considered progression of non-target lesions in the presence of measurable disease, unequivocal progression is defined as substantial worsening in non-target disease such that, even in the presence of SD or PR in target disease, the overall tumor burden has increased sufficiently to merit discontinuation of the therapy.

### **Special Consideration**

*Lesions by clinical examination* will not be used for response in this study.

#### *Cystic lesions*

- Cystic lesions that meet the criteria for radiographically defined simple cysts should not be considered as malignant lesions (neither measurable nor nonmeasurable) since they are, by definition, simple cysts.
- Cystic lesions thought to represent cystic metastases can be considered as measurable lesions, if they meet the definition of measurability described above. However, if noncystic lesions are present in the same subject, these are preferred for selection as target lesions.

### *Bone lesions*

- Bone scan, PET scan or plain films are not considered adequate imaging techniques to measure bone lesions. Computed tomography or MRI must be used to corroborate findings by these modalities.
- Lytic bone lesions or mixed lytic-blastic lesions, with identifiable soft tissue components, that can be evaluated by cross-sectional imaging techniques such as CT or MRI can be considered as measurable lesions if the *soft tissue component* meets the definition of measurability described above.
- Blastic bone lesions are non-measurable.

### *Lesions with prior local treatment*

- Lesions situated in a previously irradiated area are not considered measurable.

## **Imaging Methods**

The same method of assessment and the same technique used to characterize each identified and reported lesions at baseline should be used during each follow-up assessment. All measurements should be taken and recorded in metric notation using a ruler or calipers. Imaging based evaluation is preferred to evaluation by clinical examination unless the lesion(s) being followed cannot be imaged but assessed by clinical examination (referring to biopsy-proven visible lesion(s) on the chest).

Chest x-ray: Chest x-ray will not be used for response assessment in this study.

Conventional CT and MRI: This guideline has defined measurability of lesions on CT scan based on the assumption that CT slice thickness is 5 mm or less. If CT scans have slice thickness greater than 5 mm, the minimum size for a measurable lesion is twice the slice thickness. MRI is also acceptable in certain situations (eg, for body scan) except for lung.

Use of MRI remains a complex issue. MRI has excellent contrast, spatial, and temporal resolution; however, there are many image acquisition variables involved in MRI, which greatly impact image quality, lesion conspicuity, and measurement. Furthermore, the availability of MRI is variable globally. As with CT, if an MRI is performed, the technical specifications of the scanning sequences used should be optimized for the evaluation of the type and site of disease. Furthermore, as with CT, the modality used at follow-up should be the same as was used at baseline and the lesions should be measured/assessed on the same pulse sequence. It is beyond

the scope of the RECIST guidelines to prescribe specific MRI pulse sequence parameters for all scanners, body parts, and diseases. Ideally, the same type of scanner should be used and the image acquisition protocol should be followed as closely as possible to prior scans. Body scans should be performed with breath-hold scanning techniques, if possible.

Positron emission tomography will not be used for response assessment in this study.

Ultrasound: Ultrasound will not be used for response assessment in this study.

Bone scans: CT or MRI scan will be used to confirm results of bone scans. Preferred method for confirmation is MRI.

Tumor Markers: Tumor markers may be evaluated for changes but will not be used to determine PD in this study.

Cytology, Histology: The cytological confirmation of the neoplastic origin of any effusion that appears or worsens during treatment when the measurable tumor has met criteria for response or SD will be considered malignant unless cytologically confirmed.

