#### **5.7.6.5 Blinded Independent Radiology Committee**

For the purpose of evaluating the radiographic study endpoints and to minimize the potential for differential dropout in the placebo arm, a BIRC will be employed in a real-time dual-reader adjudicated fashion.

All radiological studies acquired at all scheduled time points and any additional (unscheduled) radiological images acquired for tumor lesion assessment must be sent to the BIRC in original DICOM format (as detailed in the Site-specific Imaging Core Manual) promptly after acquisition. Electronic transfer of scan files (via FTP, HTTP, or similar means) is required. For this study paper or film will be unacceptable, as will transfer of physical media files. The site is expected to maintain a copy of digital data for the retention period applicable to the protocol, GCPs, and federal, international and/or state legal and medical requirements. The Sponsor and/or designee will retain the media for the life of the study.

Prior radiation history will be sent to the BIRC for the purpose of valid identification of target lesions. The BIRC will review all images per RECIST 1.1 in a central, blinded, and independent fashion.

BIRC evaluations of each radiographic time point are to be completed promptly after receipt of a complete set of images that meet quality requirements defined in the study imaging manual.

At the time of investigator-determined radiographic progression per RECIST 1.1, investigators may request from the Sponsor's medical monitor (or designee) confirmation of BIRC-determined radiographic PD. Only confirmation that BIRC-determined radiographic progression has been documented (or not) will be provided to the investigator. The BIRC readers will not be notified of these requests from the investigator, nor will the BIRC readers be informed of the nature of the investigator evaluation.

Further details are provided in the study imaging charter.

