### **Time Point Assessments**

The frequency and schedule of tumor assessments is defined in the protocol. The schedule is to be maintained regardless of whether study treatment is given, reduced, held, or discontinued, including for subjects randomized to placebo who cross over to receive cabozantinib (Appendix B).

At baseline, tumors and lymph nodes are classified and documented as target or nontarget lesions per the definitions provided above. It is possible to record multiple nontarget lesions involving the same organ as a single item (eg, ‘multiple liver metastases’). At all postbaseline (follow-up) evaluations the baseline classification (target, nontarget) is to be maintained and lesions are to be documented and described in a consistent fashion over time (eg, recorded in the same order on source documents).

At each assessment, a sum of the diameters (longest for nonnodal lesions, short axis for nodal lesions) for all target lesions will be calculated and included in source documents. The *baseline sum of the diameters* (SoD) will be used as reference to further characterize any objective tumor regression in the measurable dimension of the disease. The lowest SoD (nadir) since (and including) the baseline value will be used as reference for evaluating progression.

After baseline, target lesions should have the actual size documented, if possible, even if the lesions become very small. If in the opinion of the radiologist the lesion has likely disappeared, 0 mm should be recorded. If the lesion is present but too small to measure, an indicator for ‘too small to measure’ should be included in source documents.

Nontarget lesions are to be assessed qualitatively (present, resolved, or unequivocal progression) and new lesions, if any, are to be documented separately.

At each evaluation, progression status is to be determined based upon the time point status for target lesions, nontarget lesions, and new lesions.

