**New Lesion Time Point Response (TPR)**

---

|            |  |
|------------|--|
| Yes | 

Lesion present at follow-up visit either for the very first time or re-appearing (ie, lesion was present at baseline, disappeared at a follow-up visit and re-appeared later). Confirmation of bone scan findings must be obtained by performing CT or MRI of the area of concern. Preferred method for confirmation is MRI.

 |
| No  | 

No new lesions present at follow-up.

   |

---

CT, computed tomography; MRI, magnetic resonance imaging.

---

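### The effusion sentence in protocol Appendix H contradicts itself and, taken literally, presumes an untested effusion malignant, so a new benign effusion could be read as BIRC progression

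*Combined protocol and SAP*

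**What the plan says.** The rule is a single sentence in protocol Appendix H, Imaging Methods, under Cytology, Histology. Its parts, in order:

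- Subject: "The cytological confirmation of the neoplastic origin of any effusion that appears or worsens during treatment"
- Scope: "when the measurable tumor has met criteria for response or SD"
- Rule: "will be considered malignant unless cytologically confirmed"

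No other section of the protocol or SAP states a rule for effusions. The rest of Appendix H determines what the label leads to:

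- Definitions lists effusions among the nonmeasurable lesions ("Bone lesions, leptomeningeal disease, ascites, pleural/pericardial effusions"). Non-target disease is defined as "All other lesions (or sites of disease) including all non-measurable lesions".
- Under Time Point Assessments, "progression status is to be determined based upon the time point status for target lesions, nontarget lesions, and new lesions".
- The new-lesion table counts a "Lesion present at follow-up visit either for the very first time or re-appearing". The overall response table assigns PD whenever there is a new lesion.
- Time Point Assessments also says that a new lesion should not be a finding believed to be something other than tumor.
- Definitions and the non-target table require non-target progression to be unequivocal and to reflect overall disease, not growth of one lesion.

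On central reading, protocol Section 5.7.6.5 says: "The BIRC will review all images per RECIST 1.1 in a central, blinded, and independent fashion". Sections 5.7.6.5 and 11.3 name scans and prior radiation history as the material reviewed, and leave further detail to the imaging and BIRC charters.

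**The concern.** The only confirmation the sentence names is confirmation that the effusion is neoplastic, and that is the condition under which it stops calling the effusion malignant. The test is reversed. The one default it states, for an effusion nobody has sampled, is malignant. The Appendix A schedule contains no effusion cytology, so unsampled effusions are to be expected.

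The sentence applies exactly where it can change the answer: measurable tumor is in response or SD, and the effusion decides between that status and PD. BIRC progression is a primary PFS event (SAP Section 8.1.2.4). The first overall PD also closes the window for best overall response (SAP Section 8.1.1.1), which feeds the BIRC-based ORR test (SAP Section 8.1.1.4).

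Readers and sites that silently repair the sentence may repair it in opposite directions and code the same finding differently. The investigator-read sensitivity analysis (PFS-EP-3) gives no independent check on this rule, because it too uses RECIST 1.1, for which Appendix H is the protocol's text.

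**Working it through.** No stated figure depends on this sentence, so the check is mainly of text.

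**Step 1: what the sentence does with each kind of effusion.** Three readings are set side by side. The second supplies a missing word (benign) at the end. The third follows the sentence's own opening.

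| Effusion, measurable tumor in response or SD | Literal text | If benign is supplied | Consistent with the opening |
|---|---|---|---|
| No cytology | malignant | malignant | not presumed malignant |
| Cytology neoplastic | exempted | malignant | supports progression |
| Cytology benign | malignant (neoplastic origin not confirmed) | not malignant | not progression |

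The literal column is wrong in the second and third rows and presumes malignancy in the first. The other two readings agree on tested effusions and give opposite defaults for untested ones.

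**Step 2: from label to PD.** The sentence says malignant; it does not say PD. PD must come through target, non-target or new-lesion status.

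- New effusion: a nonmeasurable lesion seen for the first time, hence a new lesion, hence overall PD. The check on this path is the instruction to leave out findings believed not to be tumor. The effusion sentence presumes the opposite, so the two conflict.
- Worsening pre-existing effusion: a non-target lesion. The malignant label alone does not satisfy the requirement for unequivocal, overall worsening, so that test still stands in the way.

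**Step 3: from PD to the endpoints.**

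- PFS: BIRC PD is an event. A benign effusion coded PD is an early event if the subject would have progressed later, and a false one if the subject would otherwise have been censored.
- ORR: a response counts only if confirmed at least 28 days later and before the first PD. A benign effusion costs a response only if it is coded PD before confirmation.

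**Step 4: size.** The documents give no effusion rate, overall or by arm. The figures below show sensitivity to assumed inputs and are not estimates.

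PFS: let s be a false-progression hazard, equal in both arms, as a share of the placebo hazard. Then HR = (0.61 + s)/(1 + s), and Schoenfeld power at 193 events, 2:1 allocation and two-sided 0.04 is Φ(√(193 × 2/9) × |ln HR| − 2.054). With s = 0 this gives 6.549 × 0.4943 − 2.054 = 1.183, or 88.2%, against the plan's 90%. The change from that baseline is what matters here.

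| s (assumed) | HR | Power |
|---|---|---|
| 0 | 0.610 | 88.2% |
| 0.02 | 0.63/1.02 = 0.618 | 86.5% |
| 0.05 | 0.66/1.05 = 0.629 | 83.8% |
| 0.10 | 0.71/1.10 = 0.645 | 79.2% |

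ORR: exact Fisher power at two-sided 0.01 with 33 placebo and 67 cabozantinib subjects, 2% versus 35%, is 97.0% (the plan says above 90%). If 5%, 10% or 20% of cabozantinib responses were lost before confirmation, ORR would be 33.3%, 31.5% or 28.0%, and power 95.3%, 92.8% or 84.6%.

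**The case against.** The strongest reply is that the sentence is a drafting slip that trained readers will see through, and that Appendix H already protects against misuse. Much of this stands. A reader who believes an effusion is benign has grounds under Time Point Assessments not to call it a new lesion, and a worsening old effusion must meet the unequivocal-progression test. Investigators are also told in Section 5.7.6.1 to delay calling progression when findings are ambiguous. What does not stand is that these cure the sentence. The only rule specific to effusions presumes malignancy while the general rule leaves the matter to judgment, and nothing says which prevails.

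A second reply is that the BIRC charter may settle it. That is fair. A reader might infer from Sections 5.7.6.5 and 11.3 that cytology never reaches the BIRC and that the malignant default therefore operates. The documents do not show this: they are silent on cytology and defer detail to charters that are not among them. The protocol text still needs correcting, because investigators work from it.

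A third reply concerns the remedy. Making positive cytology a condition for any effusion to count would create the opposite error. With no cytology scheduled, unsampled malignant effusions would never count on their own, and site-chosen sampling would drive a radiographic endpoint. This stands and shapes the fix.

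**Conclusion.** The defect in wording is certain. The consequence is a possibility: a new benign effusion arising during response or SD could be read as a new lesion and BIRC PD, giving a false or early PFS event and, before confirmation only, a lost response. The path is weaker for a worsening pre-existing effusion.

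Three stronger conclusions might be inferred and are not supported:

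- That benign effusions will become progression in both primary endpoints. This ignores the new-lesion and non-target safeguards, and the ORR effect depends on timing.
- That a given share of events is affected. Assuming, say, that 2–5% of 300 subjects have such an effusion gives 6–15 subjects, or 6/193 = 3.1% to 15/193 = 7.8% of the target events. The rate has no anchor in the documents, and the count assumes that every such effusion is coded PD.
- That the result is biased toward one arm. Readers are blinded and no rate by arm is given. An equal false-progression hazard in both arms would dilute the effect, as in the working; an unequal one could act either way.

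Size and direction therefore cannot be stated. The conclusion rests on the literal text, on there being no other effusion rule in the documents, and on not having seen the charters. The correction is worth making because it is cheap and the sentence bears on both primary endpoints.

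**What to change.** Replace the effusion sentence in Appendix H with text to this effect: an effusion that appears or worsens while measurable tumor is in response or SD is not presumed malignant; cytology showing neoplastic origin supports counting it as progression; without cytology, a new effusion is judged under the new-lesion rule in Time Point Assessments and a worsening one under the unequivocal-progression rule for non-target lesions.

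Put the same wording in the BIRC charter, and state there and in Section 5.7.6.5 whether any cytology already obtained is forwarded to the BIRC.

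The cost is a short rewording in Appendix H and matching text in the charter and Section 5.7.6.5. If cytology is to be forwarded, existing results are added to what the BIRC receives. No new procedure, visit or sample is required.
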